6.1.2. Secondary Efficacy Endpoints

Key Secondary Endpoints:

- **Time to discharge**, defined as the difference (in hours) between the date and time of the hospital discharge order issued by a qualified health care professional and the date and time of the start of the first infusion (loading dose) of study drug, ie,

Time to Discharge (in hours)

= [Date and time of hospital discharge order] – [Start date and time of 1st infusion (loading dose) of study drug]

- **Cumulative IV opioid consumption in MEU/kg** while the subject is in the hospital, beginning from the start date and time of the first infusion (loading dose) of study drug.
 - See Appendix [Section 10.1.1](#) for derivation details.
- **Time to discontinuation of IV opioids**, defined as the difference (in hours) between the latest IV opioid stop date and time and the start date and time of the first infusion (loading dose) of study drug, ie,

Time to discontinuation of IV opioids (in hours)

= [Latest stop date and time for IV Opioids] – [Start date and time of 1st infusion (loading dose) of study drug]

Note: A bolus injection of an IV opioid and a continuous infusion of IV opioids can occur simultaneously. Therefore, care needs to be taken when identifying the latest stop date and time and/or in the imputation for missing start and/or stop time data for IV opioids.

Other Secondary Endpoints:

- *Cumulative IV opioid consumption in MEU/kg within the first 24 hours post the start of the first infusion (loading dose) of study drug.*
 - See Appendix [Section 10.1.1](#) for derivation details.
- Percent of subjects re-hospitalized for VOC within 3 days of discharge.

6.4. Covariates

Age Group (in the case of Cohort 1 and Cohort 2 combined or Cohort 1 alone) and Genotype will be used as covariates in the analysis of covariance (ANCOVA) models.

7. HANDLING OF MISSING VALUES

- Missing values for safety endpoints will not be imputed.
- For time to event and IV opioid use calculations, measurement begins from the start date and time of the first infusion (loading dose) of the study drug. If the start date and time of the first infusion of study drug (loading dose) are not available, including scenarios where the subject is randomized but not treated, the time of 12:00 (24-hr clock) on the randomization date, will be used (time of randomization is not collected as part of the study database).

- The time of discontinuation from study is not collected in the study database, therefore 23:59 (24-hr clock) on the date of discontinuation from study will be used, when the time of discontinuation from study is needed for the derivation of any endpoint.
- If the date of death is present, but the time of death is missing, 23:59 (24-hr clock) on the date of death will be used, when the time of death is needed in the derivation of any endpoint.

7.1. TTRFD

Table 6. Handling of Missing TTRFD data components and Censoring Rules

Scenario	TTRFD Censored (Yes/No)	Computation of TTRFD (in hours)
(i) C1 and/or C2 are never met For a treated subject, the date and time corresponding to C1 and/or C2 used in the computation of the censored TTRFD will be the date and time of the last RFD assessment when C1 and/or C2 are still unmet.	Yes	The dates and time for the unmet criteria from C1-C6, will be determined using Section the first column in this table. Dates and time for the met criteria from C1-C6, will be determined using Table 5 . TTRFD = STOP—START; where
(ii) C3, C4, C5, and/or C6 are never met (subject did not discontinue from the study): Start date and time of the latest IV concomitant drug administration is recorded but the stop date and time is missing. For a treated subject, if any applicable criterion among C3-C6, has the latest start date and time for the last administration (of IV concomitant drug) present but the corresponding stop date and time is missing, then that criterion is considered not met. In this case, the time corresponding to the unmet criterion, to be used in the computation of the censored TTRFD, will be the start date and time for the last administration (of IV concomitant drug).	Yes	STOP = Latest date and time among the dates and times for the met or unmet criteria from C1- C6; START = Start date and time of 1 st infusion (loading dose) of study drug.
(iii) Death before RFD criteria met If a treated subject dies in the hospital before RFD criteria are met, then TTRFD will be censored. For C1and/or C2, that was not met prior to death, the time used in the computation of censored TTRFD, will be as described in (i) above. For any of the criteria C3-C6 where death occurred prior to the recording of latest stop date and time of the corresponding IV concomitant drug, the date and time of death will be used as the date and time	Yes	

Scenario	TTRFD Censored (Yes/No)	Computation of TTRFD (in hours)
where the specific criterion was not met.		
(iv) C3, C4, C5, and/or C6 are never met due to discontinuation from the study: Start date and time of the latest IV concomitant drug administration is recorded but the stop date and time is missing.	Yes	
For a treated subject, if any applicable criterion among C3-C6, has the latest start date and time for the last administration (of IV concomitant drug) present but the corresponding stop date and time missing due to discontinuation from the study, then that criterion is considered not met. In this case, the time corresponding to the unmet criterion, to be used in the computation of the censored TTRFD, will be 23:59 on the date of discontinuation from study.		
(v) Randomized and treated subjects with no data on C1-C6	Yes	TTRFD = 0 hours.
(vi) Randomized but not treated subjects [need to check if there is IV concomitant drug use based on eCRF data at or after 12:00 (24-hr clock) on the randomization date]	Yes	TTRFD = STOP—START; where
In the case of missing stop date/time in any of C3-C6 due to discontinuation from the study, the criterion is considered not met. The date/time of the unmet criterion will be 23:59 on the date of discontinuation from study.		STOP = Latest date and time among the dates and times for the met or unmet criteria from C3- C6 (data are not collected on C1 and C2 for untreated subjects);
For subjects who have no IV concomitant drug use based on eCRF data at or after 12:00 (24-hr clock) on the date of randomization, the criterion C3 is considered met at 12:00 (24-hr clock) on the date of randomization. Criteria C4-C6 are considered NA.		For subjects who have IV records at or after 12:00 (24-hr clock) on the date of randomization:
(vii) C3, C4, C5, C6: Latest stop date present, stop time missing	No	START = 12:00 (24-hr. clock) on the date of randomization
If the stop time is missing, but the corresponding stop date (for any IV concomitant drug administration) is available, the missing stop time will be imputed at 23:59 (24-hr clock), and this criterion will be considered met.		For subjects who have no IV records at or after 12:00 (24-hr clock) on the date of randomization:

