5.8.4. Pain Management

Pain management should follow the usual standard of care considering the institution's usual procedures and determined by the sickle cell disease clinical team which may include the hematologist, emergency medicine staff, pain specialist, hospitalist and nurse coordinator. Specific medications, dosing and infusion parameters should be individualized according to the subject's acute pain characteristics taking into account past medical history, concomitant medications, concurrent clinical concerns, and protocol restrictions as noted in [Section 5.8.2](#).. The following suggestions are offered to standardize management:

- Recommended IV pain medications include, but are not limited to, morphine, hydromorphone, ketorolac, or fentanyl, used in accordance with standard clinical practice. Study site staff should contact Pfizer's medical monitor when considering medications not included in this list;
- Initial treatment should aim to achieve pain control; pain control is defined as pain that does not require further escalation of pain medication OR subject reports pain is controlled;
- Ongoing treatment should aim to maintain pain control; consider weaning IV opioids once pain is controlled;
- Patient-controlled analgesia (PCA) use (basal and bolus dosing) is encouraged for all subjects, per hospital procedure;
- In addition to IV pain medications, subjects should receive other supportive care and treatments according to standard of care. These may include, but are not limited to, the following:
 - adequate hydration per routine procedure;
 - incentive spirometry at regular intervals and/or other respiratory therapies (which are highly encouraged);
 - supplemental oxygen
 - adjunctive mechanical treatments such as massage, application of heat packs, etc.

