9.2.1. Analysis of Primary Endpoint

The primary endpoint is time to readiness-for-discharge from the hospital. Time to readiness-for-discharge is defined as the difference between the readiness-for-discharge date and time (see [Section 7.1.1](#) for detail) and the start date and time of the first infusion of study drug in hours.

Below are examples of scenarios where subjects receive an infusion of study drug but do not meet the primary endpoint criteria:

- If one or more applicable criteria are not met for a subject before the subject is discharged or are missing, then the time to readiness-for-discharge will be treated as censored. If a subject dies in the hospital before all criteria are met, then the time to readiness-for-discharge will be treated as censored.
- If a subject is not hospitalized and prematurely terminates from the study before all criteria are met, the time to readiness-for-discharge will be treated as censored. If a subject is randomized but not infused with study drug, the time to readiness-for-discharge will be defined as the time from randomization to the time of the subject's termination and will be treated as censored.

Details on censoring rules for the time to readiness-for-discharge are provided in the SAP.

The primary analysis will be performed using the Cohort 1 and Cohort 2 populations combined, as well as Cohort 1 and Cohort 2 populations separately. The primary analysis to test the difference between the rivipansel and placebo groups will utilize a stratified log-rank test where the stratifications are age group (Cohort 1 and Cohort 2 combined or Cohort 1 only) and genotype. For Cohort 2, a log-rank test stratified by genotype will be performed.

A Cox regression model with age group (Cohort 1 and Cohort 2 combined or Cohort 1 only) and genotype as stratification variables will be used to estimate the treatment group hazard ratio and the corresponding two-sided 95% confidence interval. Median Time to readiness-for-discharge will be estimated using the Kaplan-Meier product limit method.

The number and percent of subjects who are documented to have achieved the event of readiness-for-discharge, as well as the number and percent of subject who were censored will be reported for each of the treatment groups.

Multiple sensitivity analyses will be conducted and will be fully described in the SAP.

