7.4. Time to discontinuation of IV opioids

Time to discontinuation of IV opioids is defined as the difference in hours between the time and date of completion of the last administration of IV opioid and the time and date of initiation of the first infusion (loading dose) of study drug. A bolus injection of an IV opioid and a continuous infusion of IV opioid can occur simultaneously. Therefore, care needs to be taken when identifying the date and time of completion of the last administration of IV opioid.

Table 8. Handling of Missing Data and Censoring Rules for Time to Discontinuation of IV opioids

Scenarios	Censored? (Yes/No)	Computation of Time to Discontinuation of IV opioid (in hours)
(i) Death	Yes	
Time to discontinuation of IV opioids
 
= STOP – START; where
 
STOP = Date and time of subject's death
 
START = Date and time of start of the first infusion (loading dose) of study drug

(ii) Latest IV opioid start date and time are recorded. Stop date is recorded but stop time is missing	No	
Time to discontinuation of IV opioids
 
= STOP – START; where
 
STOP = 23:59 on the recorded date of the last IV opioid if the latest IV opioid is a continuous infusion OR STOP = 15 minutes after the start time if the latest IV opioid is a bolus injection.
 
START (for treated subjects) = Date and time of the start of the first infusion (loading dose) of study drug.
 
START (for randomized but not treated subjects) = 12:00 (24 hr. clock) on the date of randomization.

(iii) Latest IV opioid has start date and time recorded but stop date and time are missing (subject did not discontinue from study)	Yes	
Time to discontinuation of IV opioids
 
=STOP – START; where
 
STOP = Start date and time of latest IV opioid.
 
START (for treated subjects) = start date and time of the first infusion (loading dose) of study drug.
 
START (for randomized but not treated subjects) =

Scenarios	Censored? (Yes/No)	Computation of Time to Discontinuation of IV opioid (in hours)
(iv) Subject does not have any IV opioid data recorded.	No	12:00 (24 hr. clock) on the date of randomization.
(v) Discontinuation from study	Yes	
Time to discontinuation of IV opioids
 
=STOP — START =0 hours; where

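### The missing-stop rules in SAP Tables 6 and 8 look at the latest-starting IV record, while the endpoints end at the latest stop, so overlapping records can be misdated

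*SAP*

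**What the plan says.** **When IV use ends.** SAP Table 5 dates C3 at the latest IV opioid stop, and C4-C6 likewise at the latest stop of the relevant treatment. SAP 6.1.2 defines time to discontinuation of IV opioids by the same latest stop.

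**What happens when a stop is missing.**
- Table 6 (ii), treated subjects who stay in the study: a criterion among C3-C6 is unmet if it "has the latest start date and time for the last administration (of IV concomitant drug) present but the corresponding stop date and time" is missing. The criterion is then timed at that record's start and TTRFD is censored.
- Table 6 (iv), discontinuation: the same latest-start key, the start being "present but the corresponding stop date and time missing due to discontinuation from the study, then that criterion is considered not met". The time becomes 23:59 on the discontinuation date.
- Table 6 (vii): if only the stop time is missing and "the corresponding stop date (for any IV concomitant drug administration) is available", the time is set to 23:59 and the criterion counts as met. This row is not tied to the latest start.
- Table 8 (ii), stop time missing on the latest IV opioid: an event, with "STOP = 15 minutes after the start time if the latest IV opioid is a bolus injection".
- Table 8 (iii): "Latest IV opioid has start date and time recorded but stop date and time are missing". The subject is censored at that record's start.

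**Overlap.** Protocol 5.8.4 states: "Patient-controlled analgesia (PCA) use (basal and bolus dosing) is encouraged for all subjects". SAP 6.1.2 and 7.4 both note that a bolus and a continuous infusion of IV opioid can run at the same time, and ask for care. Neither section turns this into a rule.

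**Censoring principle.** Protocol 9.2.1 treats TTRFD as censored "If one or more applicable criteria are not met for a subject before the subject is discharged or are missing".

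**The concern.** The end of treatment is ordered by stop, but the test for an incomplete record is ordered by start. If records run one after another, the record with the latest start also has the latest stop, and the two keys agree. If a long infusion overlaps short boluses, they need not agree.

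Two errors then follow from the text. A wholly blank stop on an earlier-starting infusion is never tested, so the criterion is dated by some other record's stop and counts as met. Conversely, an incomplete stop on a short, late-starting bolus decides the outcome although an infusion has a later recorded stop.

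Time to discontinuation of IV opioids is fourth in the alpha-controlled sequence and takes its value straight from these rows. C3-C6 also feed the primary endpoint. Even where few subjects are affected, two programmers following the SAP could derive different statuses or times from the same records.

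**Working it through.** **1. Literal application.** The records are hypothetical and the loading dose is at Day 1 08:00. Day 3 20:00 is 48 + 12 = 60 h, and Day 4 10:00 is 72 + 2 = 74 h. 'Latest IV opioid' in Table 8 is read as latest start.

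| Case | Infusion (h) | Bolus (h) | Rules as written | All records considered |
|---|---|---|---|---|
| 1 | 0 to blank | 60 to 60.25 | Table 6 (ii) and Table 8 (iii) do not apply, because the bolus has a stop. C3 met at 60.25; IV opioid discontinuation is an event at 60.25 | Infusion open: not met, censored no earlier than 60.25 |
| 2 | 0 to 74 | 60 to blank (date and time) | Table 8 (iii): censored at 60. Table 6 (ii): C3 unmet, timed at 60 | No earlier than 74 |
| 3 | 0 to 74 | 60; stop date Day 3, time blank | Table 8 (ii): event at 60 + 0.25 = 60.25 | Event at 74 |
| 4 (no overlap) | 0 to 58 | 60 to blank | Censored at 60 | Censored at 60 |

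Case 2 drops 74 - 60 = 14 h of recorded IV opioid use. Case 3 places the event 74 - 60.25 = 13.75 h before a recorded stop. Case 4 shows that the problem needs overlap. In case 2, censoring is the plan's chosen treatment of a wholly blank final stop and occurs without overlap too; what overlap adds is the loss of the later recorded stop.

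**2. The same case 3 records under Table 6.** Row (vii) sets the bolus stop to Day 3 23:59, which is 63 h 59 min (63.98 h). Table 5 takes max(74, 63.98) = 74 h. So C3 is dated correctly at 74 h, while Table 8 gives 60.25 h for the end of the same IV opioids.

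**3. Two imputations for one bolus.** For that bolus, Table 6 (vii) gives 23:59 and Table 8 (ii) gives 20:15, a gap of 3 h 44 min that does not depend on overlap.

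**4. Reach into TTRFD.** The readiness date is the maximum over the applicable C1-C6, and the censored STOP is also a maximum over C1-C6. A wrong time for one criterion therefore changes TTRFD only when that criterion sets the maximum.

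**5. Size.** Neither document gives a rate of blank stops.
- Design figure (SAP 4.1: medians 156 and 106 h, two-sided alpha 0.05, power 0.90, 1:1 allocation): events = 4(1.960 + 1.282)² / [ln(106/156)]² = 4 × 10.51 / 0.3864² = 281.5, so 282. This reproduces the plan.
- Power with d events = Φ(√d × 0.3864/2 - 1.960). This gives 90.05% at 282 events. As an assumption, losing 6 events (276) gives 89.4% and losing 15 (267) gives 88.4%.
- For case 1 only, an illustrative simulation assumed IV opioid courses of 6 h plus an exponential with median 120 h, basal records from 12 h to one continuous record, and boluses every 4 to 12 h on average. A bolus started after the last basal record in 37-99% of courses. The last bolus ended 2.2 to 11.1 h before the true end on average.
- If 1-5% of 300 subjects (3 to 15) had such a blank, about 3 × 0.37 = 1 to 15 × 0.99 = 15 would be affected. All these inputs are assumptions.

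**The case against.** The SAP saw the overlap. Section 6.1.2 asks for care both in finding the latest stop and in imputing missing IV opioid times, and an event at 60.25 h in case 3 would contradict that section's own definition. 'Latest IV opioid' in Table 8 is also undefined, so a careful programmer might avoid cases 2 and 3. This stands in part. But a wholly blank stop cannot be ordered by stop, so latest start is the natural reading of row (iii). The caution gives no rule, covers IV opioids only and does not reach C4-C6. SAP 7.3 does not help: its carry-over between infusions needs a recorded stop date and serves the consumption endpoints, and for a missing final stop it refers back to Table 8.

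Three stronger readings are tempting, and the documents do not support them.
- *Every missing stop in both tables is judged on the latest start.* Table 6 (iii), (vi) and (vii) and Table 8 (i) and (v) are not so keyed. Row (vii) already handles time-only gaps in TTRFD, so case 3 does not touch the primary endpoint.
- *C4-C6 are unprotected whereas C3 is masked by C1.* The maximum over C1-C6 can mask an early time for any of them.
- *The simulated percentages are expected rates.* The protocol records IV opioids about every 4 hours for 48 hours and then daily, and does not show that each patient-controlled bolus becomes its own timed record. The SAP's list of Version 5 changes calls missing start or stop times with dates present rare.

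Most of the sensitivity analyses in SAP 8.2.3 are redacted, so whether they vary this handling cannot be judged.

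**Conclusion.** The mismatch is real in the operative text. Table 6 (ii)/(iv) and Table 8 (ii)/(iii) test one record chosen by start, while the endpoints are defined by the latest stop. With overlapping records, a wholly blank infusion stop can be passed over, and in Table 8 an incomplete bolus stop can override a later recorded infusion stop. The Table 8 part rests on reading 'latest' as latest start.

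Time to discontinuation of IV opioids is directly exposed. TTRFD is exposed only for stops with both date and time blank, and only when that criterion sets the maximum over C1-C6.

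The number of affected subjects is unknown and probably small. A reader might infer a biased treatment comparison or a material loss of power. The documents support neither: no direction between arms is expected, and even 15 lost events would leave power at 88.4%. This is a minor correction to the derivation and its reproducibility.

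**What to change.** Amend Table 6 (ii)/(iv) and Table 8 (ii)/(iii) before unblinding:

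- **(a)** Evaluate all records for the criterion. Where it is met, date it at the latest recorded or imputed stop across records.
- **(b)** Never censor earlier than the latest recorded start or stop of any record.
- **(c)** Treat an earlier-starting infusion with a wholly blank stop as unmet only if no later record of the same infusion or drug shows that it ended. A blanket rule that any open infusion record makes the criterion unmet would go too far: one unresolved Day 1 fluid or antibiotic blank would censor a subject whose later records show that it ended, and the design leaves room for only 300 - 282 = 18 non-events.
- **(d)** Use one imputation for a bolus with a missing stop time, reconciling 23:59 in Table 6 (vii) with start plus 15 minutes in Table 8 (ii). Also say whether a bolus with a wholly blank stop is imputed or left open. Under (a) and (b), case 2 then becomes an event or a censoring at 74 h, not at 60 h.

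The cost is a few lines of SAP text and derivation code, with no new data, and possibly a few more censored subjects. SAP section 1 records that the study team has remained blinded, so the change can still be made without knowledge of treatment.

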7.2. Time to Discharge

Table 7. Handling of Missing Data and Censoring Rules for Time to Discharge

Scenarios	Censored? (Yes/No)	Computation of Time to Discharge (in hours)
(i) Death prior to issue of discharge order Subject dies in the hospital prior to issue of the hospital discharge order.	Yes	
Time to discharge
 
= (Date and time of subject's death) — (Date and time of start of the first infusion [loading dose] of study drug)

(ii) Discharge order date present, discharge order time missing If the discharge order date is present but the discharge order time is missing, the missing time will be imputed as 23:59 on the date of the discharge order.	No	
Time to discharge
 
= (23:59 [24-hr clock] on the date of the discharge order)
 
— (Date and time of start of the first infusion [loading dose] of study drug)

(iii) Randomized, treated or untreated subjects who are not hospitalized	Yes	
Time to discharge = 0 hours

(iv) Subject discontinuation from study resulting in missing discharge order date and time	Yes	
For randomized and treated subjects:
 
Time to discharge
 
= (23:59 on the date of discontinuation from study)
 
— (Date and time of start of the first infusion of study drug)
 
For randomized subjects who are not treated:
 
Time to discharge
 
= (23:59 on date of discontinuation from study)
 
— (12:00 [24 hr. clock] on the date of randomization)

